Aim 1: Prior to the start of our intervention, all probands will be mailed a consent letter describing the study, a questionnaire, a response card and a copy of the family invitation letter. The questionnaire will capture data on the period of time since their return of results, including, the extent to which they shared results with family members, health behaviors (i.e. are they taking preventative therapy, if indicated) and how the results have impacted them. With the proband's permission, invitation letters will be mailed to their first degree relatives to offer study participation including the intervention (free, in-home, saliva-based genetic testing) and completion of questionnaires about their experiences with genetic testing. The proband can decide to enroll their minor children who still live at home in the cascade screening (Screening only for children under age 18 with specified consent/assent). We will offer the intervention for approximately 9 months, then we will repeat the mailed questionnaires assessing uptake, disclosure, health behaviors, and general impact of the intervention.

We will compare outcomes before the implementation of our intervention (the 'traditional' cascade screening period) and after (the 'simplified' cascade screening period). Our primary outcome addresses the question of whether our simplified cascade screening intervention improves uptake of screening. Our secondary outcomes assess whether, with access to simplified screening (1) probands will tell more family members, who may or may not choose to get screened, (2) informed family members are more likely to get tested, and (3) identifying more individuals with the KCNQ1 variant actually results in more beta-blocker prescriptions since the Amish typically take very few prescription medications. The tertiary outcomes are demographic characteristics associated with uptake of cascade screening or uptake of preventative therapy.

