Our primary outcome is the rate of uptake of cascade screening before ('traditional') versus after ('simplified') the intervention. Uptake for this outcome is defined as the proportion of first degree family members (i.e. offspring and siblings) of the initial 88 probands who undergo cascade screening out of all eligible first degree family members (as defined by the Fisher book). We will compare the proportion before versus after the simplified screening approaches. Any individuals who undergo screening before the intervention will no longer be eligible for screening with the simplified cascade screening so the denominator will decrease accordingly. We have chosen to use the denominator of all first degree relatives defined by the Fisher book because this number is not dependent on participants returning the surveys where they will provide information on how many family members they told (and how many they have). Our secondary outcome includes the proportion of informed relatives who get screened. The number of participants screened for all outcomes will be obtained from charts (as [name] is ordering physician for all tests).

Our secondary outcomes are:

- Extent of disclosure of genotype results before and after the intervention. This outcome is defined as the number of family members (siblings and children) told (reported via survey) out of the total number of proband first degree relatives (known from the Fisher Book and asked on the survey).
- Proportion of informed first-degree relatives who get screened before and after the intervention. This outcome is defined as the number of family members tested out of the number told by probands (reported via surveys)
- The overall rate of uptake of preventative therapy among probands and family members (e.g., see a cardiologist and/or take a beta-blockers)

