Analyses of secondary outcomes (a) and (b) will occur in the same manner as the primary outcome, by comparing proportions before and after the intervention. For secondary outcome (c), we don't expect the proportion of appropriately treated carriers to be impacted by our intervention, but rather the absolute number of treated individuals would be impacted by detecting more carriers with improved cascade screening. For the disclosure outcome (a), we will compare results using the denominator based on Fisher book data and based on data reported in the survey. For the uptake of screening among those informed outcome (b), the denominator is based on the survey results (the proband will be asked who they disclosed results to and the family member will be asked if their family member told them). For the uptake of clinical recommendation outcome (c), we will use data from the participants' charts to determine whether beta-blocker therapy was indicated and prescribed. We will gather data from the survey on whether participants are following the recommendations. While we don't expect our intervention to change the proportion of individuals appropriately treated, we will compare the proportions before and after the intervention to confirm this assumption.

ID: VIEW4E02806052800  
Name: v2\_Sample Size and Data Analysis

HP-00081981

Sharing of Results\_V2

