### **B. Statistical methods with respect to each outcome**

#### **B1. Aim 1 (cascade screening intervention)**

##### **B1.1 Primary outcome**

Our primary outcome is the rate of uptake of cascade screening before ('traditional') versus after ('simplified') the intervention. Uptake for this outcome is defined as the proportion of first degree family members (i.e. offspring and siblings) of the initial 70 probands who undergo cascade screening out of all eligible first degree family members (as defined by the Fisher book). We will compare the proportion before versus after the simplified screening approaches. Any individuals who undergo screening before the intervention will no longer be eligible for screening with the simplified cascade screening so the

denominator will decrease accordingly. We have chosen to use the denominator of all first degree relatives defined by the Fisher book because this number is not dependent on participants returning the surveys where they will provide information on how many family members they told (and how many they have). Our secondary outcome includes the proportion of informed relatives who get screened. The number of participants screened for all outcomes will be obtained from charts (as [name] is ordering physician for all tests).

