### **B1.2 Secondary outcomes**

- a. Extent of disclosure of genotype results before and after the intervention. This outcome is defined as the number of family members (siblings and children) told (reported via survey) out of the total number of proband first degree relatives (known from the Fisher Book and asked on the survey).
- b. Proportion of informed first-degree relatives who get screened before and after the intervention. This outcome is defined as the number of family members tested out of the number told by probands (reported via surveys)
- c. The overall rate of uptake of preventative therapy among probands and family members (e.g., see a cardiologist and/or take a beta-blockers)

Analyses of secondary outcomes (a) and (b) will occur in the same manner as the primary outcome, by comparing proportions before and after the intervention. For secondary outcome (c), we don't expect the proportion of appropriately treated carriers to be impacted by our intervention, but rather the absolute number of treated individuals would be impacted by detecting more carriers with improved cascade screening. For the disclosure outcome (a), we will compare results using the denominator based on Fisher book data and based on data reported in the survey. For the uptake of screening among those informed outcome (b), the denominator is based on the survey results (the proband will be asked who they disclosed results to and the family member will be asked if their family member told them). For the uptake of clinical recommendation outcome (c), we will use data from the participants' charts to determine whether beta-blocker therapy was indicated and prescribed. We will gather data from the survey on whether participants are following the recommendations. While we don't expect our intervention to change the proportion of individuals appropriately treated, we will compare the proportions before and after the intervention to confirm this assumption.

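### Secondary outcome (b) leaves its 'after' denominator undefined and does not require the relatives tested to be among the relatives told

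*Combined protocol and SAP*

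**What the plan says.** SAP B1.2 names outcome (b) as "Proportion of informed first-degree relatives who get screened before and after the intervention" and then gives the ratio: "This outcome is defined as the number of family members tested out of the number told by probands (reported via surveys". The protocol repeats this under Sample Size and Data Analysis, item 2.

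The two halves of the ratio have different sources:
- **Denominator.** For (b), "the denominator is based on the survey results". Probands are asked whom they told, and relatives are asked whether they were told.
- **Numerator.** SAP B1.1 states: "The number of participants screened for all outcomes will be obtained from charts".

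On analysis, both documents say: "Analyses of secondary outcomes (a) and (b) will occur in the same manner as the primary outcome, by comparing proportions before and after the intervention". The primary outcome has a rule for people already tested: "Any individuals who undergo screening before the intervention will no longer be eligible for screening with the simplified cascade screening so the denominator will decrease". That rule is written for the list of first-degree relatives taken from the Fisher book.

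On timing, the protocol (Justification, Objective, & Research Design, item 2, Aim 1) has the baseline proband questionnaire cover the time since return of results. After about nine months of the intervention, "then we will repeat the mailed questionnaires assessing uptake, disclosure, health behaviors, and general impact of the intervention". The recall period of the repeat is not given.

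**The concern.** Being told and being tested are separate events and can fall in different periods. A relative who heard of the result in the traditional period, did not take the $50 blood test, and later accepts the free saliva test is the person the intervention is meant to reach. That relative is told before and tested after. The definition does not say whether such a person belongs in the 'after' denominator, and it does not require anyone in the numerator to be in the denominator at all.

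Outcome (b) carries the study's answer to whether informed relatives become more likely to be tested. The plan says it cannot formally compare uptake before and after, and (b) is to be handled like the primary, so the raw proportions are the result. If the denominator is chosen at analysis, the same data can give very different answers, and some choices show a gain when testing behaviour has not changed.

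**Working it through.** **The plan's own figure.** The only worked example concerns the primary outcome (SAP A1; protocol Sample Size and Data Analysis, item 1). 15/500 = 3.0%; 500 − 15 = 485; 0.18 × 485 = 87.3, so 87; 87/485 = 17.9%; gain 14.9 points, against a stated mark of 15. It reproduces. No figure is given for outcome (b).

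**Set-up for (b).** Let T1 = relatives told in the traditional period, T2 = relatives newly told in the simplified period, and q = the chance per period that an informed, untested relative is tested, held equal in both periods so that there is no effect. Assume full reporting and that every tested relative was told. T1, T2 and q are assumptions, because the documents give no disclosure level.

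- Tests before: q·T1. Proportion before: q.
- Informed and untested in the second period: R = (1 − q)·T1 + T2. Tests after: q·R.

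**Three possible 'after' proportions and their false gains:**

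| Denominator | 'After' | Gain with no effect |
|---|---|---|
| Newly told only | qR/T2 | q(1 − q)·T1/T2 |
| Cumulative, both counts | (q·T1 + qR)/(T1 + T2) | q(1 − q)·T1/(T1 + T2) |
| Told and still untested | qR/R | 0 |

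**Example: T1 = 300, T2 = 50, q = 5%.** Tests before = 15, so 15/300 = 5.0%. R = 285 + 50 = 335; tests after = 16.75.
- Newly told only: 16.75/50 = 33.5%, gain +28.5 points.
- Cumulative: 31.75/350 = 9.1%, gain +4.1 points.
- Told and still untested: 16.75/335 = 5.0%, gain 0.

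**How this varies.**
- Newly told only, T1 = 300, q = 5%: T2 = 10 gives 147.5%; T2 = 100 gives +14.3 points; T2 = 200 gives +7.1.
- The newly-told-only gain passes 15 points when T2/T1 < q(1 − q)/0.15, which is 0.19 at q = 3%, 0.32 at 5% and 0.60 at 10%. With no effect, the ratio passes 100% only when T2/T1 < q.
- Cumulative, T1 = 300, T2 = 50: +4.1 points at q = 5%, +7.7 at 10%, +13.7 at 20%. This gain is always below q(1 − q), so at q = 18% it stays under 0.18 × 0.82 = 14.8 points.
- Over T1 = 150 to 350, T2 = 50 to 100 and q = 5% to 20%, the newly-told-only gain runs from 7 to 112 points and the cumulative gain from 3 to 14.

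**The plan's target counts in the same setting.** With 15 tests before and 87 after, T1 = 300 and T2 = 50, 'before' is 15/300 = 5.0%. 'After' is 87/50 = 174%, (15 + 87)/350 = 29.1%, or 87/(350 − 15) = 26.0%. This is a success scenario, not a no-effect one. It shows how far the readings differ on identical data.

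**Unlinked numerator.** Charts count every test, while told counts depend on returned surveys, and SAP B1.3 expects about 60% return. If relatives of non-returning probands are told and tested at the same rate and do not report it themselves, the ratio is inflated by 1/0.6 = 1.67. For example, 15/(0.6 × 300) = 15/180 = 8.3% instead of 5.0%. A relative who learns only from the mailed family invitation can also be tested without being reported as told by a proband.

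**The case against.** The strongest reply is that the plan already implies the right count. A relative told earlier is still informed later, so a proportion of informed relatives naturally includes them and cannot exceed 100%. Outcome (b) is to be analysed like the primary, and the primary keeps untested relatives and drops those already screened. Carried over to (b), that gives the told-and-still-untested set. Further, the protocol lists no baseline questionnaire for relatives, so their reports need not split new from earlier disclosure. The follow-up proband form, which would show whether it asks about new or all disclosure, was uploaded but is not reproduced.

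Much of this stands. A reader might infer that the plan divides second-period tests by newly told relatives only, and so will report a false gain above 15 points or a ratio above 100%. The documents do not support that: nothing prescribes such a count, and both results need assumed told numbers with few relatives newly told. Mailing family invitations could make that number larger. Nor is the 15% mark stated for (b); the plan names uptake, disclosure and medical intervention.

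What does not stand is that the reference to the primary settles the matter. The sentence explains itself only as a comparison of proportions. The removal rule belongs to a Fisher-book list in which untested relatives stay by default, whereas told status changes over time and has its own survey source. Removing people already tested does not say that people told earlier are kept. Even the favourable reading leaves charted tests unlinked to reported disclosure.

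**Conclusion.** The point holds as an undefined and unlinked measure. The plan does not fix the second-period denominator of (b) and does not require the tested to be among the told. If it is read as newly told only, unchanged testing produces a false gain of q(1 − q)·T1/T2: +28.5 points at 300 told before, 50 newly told and 5% testing, and +7.1 with 200 newly told. If both counts are cumulative, the false gain is about 4 points in the first setting. On the told-and-still-untested set it is zero, by construction, when the chance of testing per period is equal.

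These sizes rest on assumed told counts, equal testing probability per period and complete reporting. They show what the wording permits, not what the study will find. The issue concerns a secondary outcome of a pilot and leaves the primary outcome untouched. It should be corrected because (b) cannot be interpreted until its denominator is fixed.

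**What to change.** In SAP B1.2(b) and the matching protocol text (Sample Size and Data Analysis, item 2), define:

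- **Before:** of relatives told by the end of the traditional period, the share tested within that period.
- **After:** of relatives told by the end of the simplified period and not tested before it began, the share tested during it.

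Build both from one person-level list that links each relative reported as told, by proband or by the relative, to the charted test date. Report 'after' separately for relatives already told before the intervention and for those newly told. Count tested relatives with no report of being told on a separate line, outside (b).

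The cost is a few lines of text and a record linkage. The plan already asks probands whom they told and takes tests from charts; if the forms record only totals, they would need to identify the relatives. There are two drawbacks. The 'after' figure will usually look less favourable. With about 60% return expected, some tested relatives will drop out of (b), which is why they need their own count.

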**1 \* Provide the rationale and sample size calculations for the proposed target population:**

Our study is based on 88 KCNQ1 Thr224Met probands who were identified as part of another research study and chose to undergo clinical confirmation of their genotype and clinical evaluation for long QT syndrome. We cannot approach probands who chose not to undergo the return of results process. These 88 probands have over 700 first degree family members who may be eligible for cascade screening with our intervention. We can assume some of the family members have died and some may not live in Lancaster County, but a very large proportion will be eligible for testing. Due to privacy laws we cannot approach a family member without permission from the proband. With permission from the proband, we will send family letters or we will provide family letters to probands for them to share with family members. This study will compare the rate of uptake of cascade screening before and after our intervention of a simplified cascade screening program. Given that an individual who undergoes cascade screening before our intervention, during the 'traditional' period does not need to undergo testing again, we cannot statistically compare the difference in the proportion of family members who undergo cascade screening before and after the intervention or the statistical power that our study will have to detect a difference in uptake. That being said, our experience suggests that uptake of cascade screening will be very low among the Amish during the 'traditional' phase when cost, transportation, and an invasive test are barriers. This pilot study will test whether we can overcome these barriers and detect a meaningful improvement in uptake of cascade screening, disclosure to family members, and uptake of appropriate medical intervention. We will define this meaningful improvement a priori as a 15% improvement. For example, if we have 3% of eligible individuals undergo cascade screening during the traditional phase, we would deem 18% of eligible individuals getting tested a clinically meaningful increase. This would translate into 15/500 getting tested before our intervention and 87/485 getting tested after implementing our intervention. Another way of looking at this is that approximately 2-3 probands would initiate cascade screening before the intervention and 12-13 would after the intervention (assuming 7 children per proband).

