## **STATISTICAL DESIGN AND STUDY POWER**

### **A. Power Calculations**

#### **A1. Aim 1 (cascade screening intervention)**

Our study is based on 70 *KCNQ1* Thr224Met probands who were identified as part of another research study and chose to undergo clinical confirmation of their genotype and clinical evaluation for long QT syndrome. We cannot approach probands who chose not to undergo the return of results process. These 70 probands have over 700 first degree family members who may be eligible for cascade screening with our intervention. We can assume some of the family members have died and some may not live in Lancaster County, but a very large proportion will be eligible for testing. Due to privacy laws we cannot approach a family member directly who has not first been contacted by the proband. We will provide family letters to probands for them to share with family members, but this is a personal decision for each proband. This study will compare the rate of uptake of cascade screening before and after our intervention of a simplified cascade screening program. Given that an individual who undergoes cascade screening before our intervention, during the 'traditional' period does not need to undergo testing again, we cannot statistically compare the difference in the proportion of family members who undergo cascade screening before and after the intervention or the statistical power that our study will have to detect a difference in uptake. That being said, our experience suggests that uptake of cascade screening will be very low among the Amish during the 'traditional' phase when cost, transportation, and an invasive test are barriers. This pilot study will test whether we can overcome these barriers and detect a *meaningful* improvement in uptake of cascade screening, disclosure to family members, and uptake of appropriate medical intervention. We will define this meaningful improvement *a priori* as a 15% improvement. For example, If we have 3% of eligible individuals undergo cascade screening during the traditional phase, we would deem 18% of eligible individuals getting tested a clinically meaningful increase. This would translate into 15/500 getting tested before our intervention and 87/485 getting tested after implementing our intervention. Another way of looking at this is that approximately 2-3 probands would initiate cascade screening before the intervention and 12-13 would after the intervention (assuming 7 children per proband).

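### Preventive-therapy outcome (c) falls under the a priori 15% improvement although its proportion is expected to stay flat, and the planned before/after comparison cannot confirm that it does

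*Combined protocol and SAP*

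**What the plan says.** **Threshold.** The protocol (Sample Size and Data Analysis, item 1) and SAP A1 name three outcomes on which the pilot should detect a meaningful gain. In the SAP this is an "improvement in uptake of cascade screening, disclosure to family members, and uptake of appropriate medical intervention". The size follows at once, here from the protocol: "uptake of appropriate medical intervention. We will define this meaningful improvement a priori as a 15% improvement". The only illustration is for screening: "This would translate into 15/500 getting tested before our intervention and 87/485 getting tested after implementing our intervention".

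**Expectation.** For outcome (c), the protocol (Sample Size and Data Analysis, item 2) and SAP B1.2 state "we don't expect the proportion of appropriately treated carriers to be impacted by our intervention". What should move is different: "the absolute number of treated individuals would be impacted by detecting more carriers with improved cascade screening". The Lay Summary and the Aim 1 design text agree. They ask whether finding more carriers leads to more prescriptions.

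**Comparison.** The protocol and SAP B1.2 then add "we will compare the proportions before and after the intervention to confirm this assumption". The outcome itself is "The overall rate of uptake of preventative therapy among probands and family members". The beta-blocker part comes from participants' "charts to determine whether beta-blocker therapy was indicated and prescribed", and the survey supplies whether recommendations are followed. Neither document gives an interval, margin or decision rule for (c).

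**The concern.** There are two separate faults.

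First, the threshold and the expectation do not fit together. A 15% improvement is set for an outcome whose proportion is expected not to improve, and the 15% is never tied to the number treated. An analyst who follows the sample-size text could report (c) as falling short of a target that the plan does not expect it to reach.

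Second, a before/after comparison with no interval or margin cannot confirm no change. A small difference is compatible with a real one. The quantity compared is also not pinned down. The definition speaks of probands and family members, the expectation of carriers, and the comparison of individuals appropriately treated. Nothing says who counts before and who counts after. If the same probands sit in both periods, the overall rate is dominated by people whom the intervention did not find. It could then look unchanged while newly found carriers are treated clearly less, or more, often than known ones.

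**Working it through.** **1. The plan's own figure.** 15/500 = 3.0%; 0.18 × 485 = 87.3, given as 87; 87/485 = 17.9%. The figure reproduces. A relative 15% would take 3% only to 3.45%, so the scale is percentage points. The example concerns screening only, and there is no stated figure for (c) to reproduce.

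**2. Inputs.**
- Tested: 15 before and 87 after (the illustration).
- Carrier risk in first-degree relatives: 50% (protocol, preliminary data).
- Probands: 88 in the protocol, 70 in the SAP. Both are shown.
- Assumed, because the documents give no value: 20-50% of carriers treated.
- Inferred from the baseline and post-intervention proband questionnaires (Surveys/Questionnaires, item 1): known carriers count in both periods.
- Simplifications: all carriers are counted, known and new carriers are treated as independent, and family clustering is ignored.

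**3. Carriers and dilution.** Relatives found before: 15 × 0.5 = 7.5. Newly found: 87 × 0.5 = 43.5.

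| | 88 probands | 70 probands |
|---|---|---|
| Known carriers | 88 + 7.5 = 95.5 | 70 + 7.5 = 77.5 |
| After pool | 95.5 + 43.5 = 139 | 77.5 + 43.5 = 121 |
| Share newly found | 43.5/139 = 31.3% | 43.5/121 = 36.0% |
| 15-point gap in new carriers, seen overall | 15 × 0.313 = 4.7 points | 15 × 0.360 = 5.4 points |
| Gap in new carriers needed to move the overall rate 15 points | 15 × 139/43.5 = 48 points | 15 × 121/43.5 = 42 points |

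Example with 88 probands and 30% of known carriers treated. The overall rate after is (0.30 × 95.5 + q × 43.5)/139, where q is the proportion of new carriers treated. For q = 15%, 30% and 45% it is 25.3%, 30.0% and 34.7%.

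**4. Precision from chart data.** The 95% half-width for new versus known carriers is 1.96 × √[p(1−p)(1/43.5 + 1/n known)].
- 88 probands: 14.3 points at p = 0.2, 16.4 at 0.3, 17.9 at 0.5.
- 70 probands: 14.9, 17.0, 18.6.

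If known carriers' care does not change, the overall before/after difference is the new share times the new-minus-known difference. Its half-width scales in the same way: 4.5-5.6 points (88) or 5.3-6.7 (70). Counting only carriers with therapy indicated would widen all of these.

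**5. The count.** At 20% treated and 88 probands, the cumulative number treated goes from 0.2 × 95.5 = 19.1 to 0.2 × 139 = 27.8. Counted by the period in which carriers were found, it is 19.1 and then 0.2 × 43.5 = 8.7. The direction depends on a rule that the plan does not state.

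**The case against.** The strongest reply is that the outcome-specific text already governs. It says twice that the proportion should not move, names the count as the effect, and illustrates the 15% for screening only. Calling (c) a failure against 15% would mean ignoring B1.2. In a self-described pilot with no test named for (c), the comparison can be read as a descriptive check. This argument stands as to weight, and it is why the point is minor. It does not remove the conflict, which is in the current text of both documents. Nor does a descriptive reading turn a small overall difference into evidence of no change.

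Four stronger readings are tempting, and the documents do not support them:
- *The overall comparison is too imprecise to exclude 15 points.* On the inferred reading it is precise enough (half-width about 4.5-6.7 points if known carriers' care is fixed). The trouble is that it answers a diluted question.
- *Relatives found in the two periods can be compared with an interval.* With 7.5 carriers before, 20% treated means 1.5 expected, too few for a normal-approximation interval to be relied on.
- *The 60% survey return in SAP B1.3 widens everything.* No baseline family-member questionnaire is listed, and Study Procedures exclude minor children from the survey. A before-period survey value for relatives is therefore not a planned measurement.
- *Outcome (c) is restricted to carriers.* The wording varies and does not settle this.

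**Conclusion.** The point holds, with minor impact. The sample-size text and the text for (c) contradict each other on whether the treated proportion should improve, and they must be reconciled. The promise to confirm no change is not supported by a comparison that lacks an interval, a margin, a fixed denominator and a period rule.

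On the inferred reading, an overall rate would shrink a 15-point difference in newly found carriers to about 5 points. The contrast that would show that difference directly has a 95% half-width of about 14 to 19 points, so even that would not usually settle the matter. These sizes rest on the plan's screening illustration, 50% carrier risk, an assumed 20-50% treated and every carrier being counted. The contradiction and the faulty inference depend on none of these. The plan does not set up a formal equivalence test or a success criterion that (c) is bound to fail, and it should not be criticised as though it did.

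**What to change.** 1. In the protocol's sample-size item 1 and SAP A1, remove outcome (c) from the 15% definition.
2. In protocol item 2 and SAP B1.2, fix one denominator: carriers with therapy indicated according to the chart. Report the number treated as the cumulative number at the end of each period. Show separately the number among carriers newly found through the intervention. State the period lengths. The intervention runs for about 9 months, while the existing data span October 2015 to October 2018, and the traditional period is not defined in the same terms.
3. Give chart-based proportions with 95% CIs for previously known carriers and for newly identified carriers. Where probands are assessed twice, report a paired before/after change. Give counts only for the few relatives found in the traditional period. Report survey-based adherence only where a survey is planned.
4. Replace the wording about confirming the assumption with: *to describe the difference with a 95% CI; absence of a difference will not be interpreted as no change*.

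The cost is wording and slightly more reporting, with no new data collection. The plan gives up a statement of no change.
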